7.2.1. Inclusion criteria

For the **characteristics cohort**, patients must meet all of the following inclusion criteria to be eligible for inclusion:

- Diagnosis of renal cell carcinoma (ICD-10: C64) during 1.1.2010-31.12.2021
- Age at least 18 years at index.
- Resident of HDSF at index.

For the **mRCC cohort**, patients must meet the following inclusion criteria in addition to the above criteria to be eligible for inclusion:

- metastatic RCC during 1.1.2010-31.12.2021; defined as
 - ICD-10 diagnosis code for metastasis (C77*-C79*), or
 - AJCC stage 4, or
 - AJCC stage data potentially not available for all patients
 - a visit to oncologist (specialty code 65) with RCC as main diagnosis, or
 - In Finland, the ICD-10 codes for metastatic disease are rarely used. In contrast, RCC patients visit oncologist, when and only when disease metastasises and therefore, the visit can be used as a proxy to a metastatic disease.
 - initiation of treatment for mRCC

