5. RATIONALE AND BACKGROUND

Renal cell carcinoma (RCC) is among the 10 most frequently occurring cancers and the most common type of kidney cancer occurring in Western communities [1]. RCCs comprise a heterogeneous group of malignant neoplasms arising from the nephron. Risk factors for RCC include obesity, hypertension, cigarette smoking, diet, diabetes, and male gender [1].

After decades of increasing trends in RCC incidence and mortality rates, it seems that rates are stabilising or starting to decline in many Western countries [1]. The worldwide number of kidney cancer cases was 431,288 (62.9% male) and deaths 179,368 (64.4% male) in 2020 [2]. Kidney cancer is more common in males compared to females. The incidence was 7.8 and mortality 3.0 per 100,000 males in high human development index countries in 2020 [2]. In Finland, the number of new kidney cancer cases was 635 in males and 353 in females in 2019 [3], and the number of prevalent patients was 4,943 males and 3,867 females in 2019 according to the Finnish Cancer Registry [4].

Localized RCC can be curatively treated with nephrectomy. However, about 20–30% of patients present with metastatic RCC (mRCC) at the time of diagnosis [5]. In addition, another 20% of patients with localized RCC undergoing nephrectomy will have a relapse and develop mRCC during follow-up. Despite the recent advances in mRCC treatment, metastatic disease is often fatal [6].

[figure not shown]
Over the last decade, the treatment of advanced/metastatic RCC has been constantly evolving, especially in the last 2-3 years with the emergence of several novel treatment options in rapid succession. Current recommendations for first-line therapy of mRCC include several combination treatments, superseding the previously recommended antiangiogenic agent monotherapies. The novel options combine an anti-PD-1-antibody with either an antiangiogenic drug (vascular endothelial growth factor receptor (VEGFR) tyrosine kinase inhibitor (TKI)), or an anti-CTLA-4-antibody. The combination treatments are recommended

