7. RESEARCH METHODS

7.1. Study design

This is a retrospective registry-based cohort investigation, utilizing existing data generated during routine clinical practice and available in the Hospital District of Southwest Finland HDSF data lake. All adult patients (age ≥ 18 years) with RCC diagnosis (C64*; '*' indicates any number) will be identified from the data lake of HDSF.

The main purpose of this study is to characterize the patient population of advanced/metastatic RCC, and their treatment patterns and treatment outcomes using medical records retrieved from HDSF data lake. The main patient stratification will be the IMDC risk category (see 8.2.3 Patient stratification). Patients with unknown risk score will be analyzed as an own patient group.

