- Treatment initiation for mRCC (sunitinib, pazopanib, cabozantinib, ipilimumab, nivolumab)

When analyzing the treatment outcomes, index is defined as the date of the treatment initiation.

End of follow-up (whichever of the following occurs first):

- Death
- Moving outside of HDSF
 - Approximated using data of healthcare contacts; no contacts to specialty care of HDSF within 2 years (patient censored at the last recorded visit)
- End of study (31.12.2021)

Length of follow-up (in years): ('end of follow-up' – 'index' + 1)/365.25

Definitions for characteristics cohort

Index:

- For mRCC patients, same as for the mRCC cohort (i.e. approximated metastasis date)
- For RCC patients, the date of the first record of RCC diagnosis (ICD-10: C64)

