7.2.2. Exclusion criteria

For the **characteristics cohort**, patients meeting any of the following criteria will be excluded from the study:

- Prevalent mRCC patients (i.e. diagnosis of metastatic RCC before 1.1.2010)
- Prevalent RCC patients (i.e. diagnosis of RCC before 1.1.2010) if there is no records of metastatic disease during 2010-2021

For the **mRCC cohort**, patients meeting any of the following criteria will be excluded from the study:

- Prevalent patients with mRCC (i.e. diagnosis of metastatic RCC before 1.1.2010)
 - Note that patients with local RCC before 2010 are included in this study if the disease has metastasised during 2010-2021
- Patients without treatment for mRCC (see Table 3 for details)

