7.3. Variables

Source for all variables is the data lake of HDSF.

Table 2. List of study variables. Abbreviations: PO=primary objective, SO=secondary objective.

Variable	Role/Relevant objective	Operational definition
ICD-10 diagnoses; RCC diagnoses	Patient inclusion/exclusion IMDC risk category	yes/no
ICD-10 diagnoses: co-diagnoses (e.g. renal insufficiency and hypertension)	PO1, SO1	yes/no; co-diagnoses before and after index
Date of birth	Patient inclusion PO1	Date; age defined at index based on birth date
Date of death	End of follow-up PO3	Date
Gender	PO1	Female/male
Home municipality	Patient inclusion End of follow-up	Home municipality at each healthcare contact
Weight	PO1	kg
Height	PO1	m
Body mass index (BMI)	PO1	derived from weight and height
Smoking status (if available in structured format)	PO1	yes/no
Outpatient visits (including emergency room visits)	Patient inclusion and index definition (visits to oncologist) SO2	Date, physician's specialty, type of arrival
Hospitalizations	SO2	Start and end dates
Procedures and operations (including nephrectomy)	PO1 SO1 SO2	Procedure code, date
Medical imaging	SO1 SO2	Imaging code, date
Medications; including - hospital medications - prescriptions	Patient inclusion/exclusion and index definition PO2 PO3 SO1 SO2	Dates, ATC-codes, active substance
Laboratory testing	IMDC risk category PO1	Dates, test id, result
Zubrod/ECOG performance status	IMDC risk category PO1	scale 0-5; converted to Karnofsky
PAD histology (if available in structured format)	PO1	
Staging of RCC, the tumor-node-metastasis (TNM) classification	Patient inclusion and index definition PO1	scale 1-4 (stages)

PFIZER CONFIDENTIAL

Table 3. List of medications for RCC treatment. ATC= Anatomical Therapeutic Chemical.

	Active substance	Brand name	ATC-code at the moment in use	ATC-code previously in use
Oral medications	axitinib	Inlyta	L01EK01	L01XE17
	everolimus	Afinitor	L01EG02	L01XE10
	cabozantinib	Cabometyx	L01EX07	L01XE26
	pazopanib	Votrient	L01EX03	L01XE11
	sorafenib	Nexavar	L01EX02	L01XE05
	sunitinib	Sutent	L01EX01	L01XE04
Intravenous medications	ipilimumab	Yervoy	L01XC11	
	nivolumab	Opdivo	L01XC17	

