7.4. Data sources

Cohort and data set formation overview is presented in Figure 2. The patient population will be selected from the health records at the data lake of HDSF based on diagnosis data and includes a personal identity code that is unique for every individual in Finland. For the identified RCC cohort, data of patient characteristics, diagnoses, healthcare contacts, treatments, laboratory and pathology tests, and performed procedures, operations and imagings will be collected from the same data lake of HDSF. The identification of the RCC cohort and collection of the additional data with personal identification numbers will be handled solely by the personnel of Auria Clinical Informatics. The identification codes are removed after linkage so that only pseudonymized data or group specific summary data is provided for analyses.

This study is conducted using existing and available clinical electronic records accessible from Auria Clinical Informatics. The study protocol and associated data request for all data will therefore be submitted to Auria Clinical Informatics for approval.

[figure not shown]

Figure 2. Overview of cohorts and data set formation.

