7.7.1. Patient characteristics

[figure not shown]
Primary objective 1:

Demographical and clinical variables of RCC and mRCC patients will be summarized at index. Treated and non-treated mRCC patients will be analysed separately. For laboratory measures and performance status, the closest available measure +/- 90 days from index will be utilized. In case of a high rate of missing values, the time window can be extended to 6 months.

The demographical and clinical variables include but are not limited to:

- age at index
- sex
- history of renal insufficiency (any records until index)
 - ICD-10 code: N17-N19
- history of dialysis (any records until index)
 - procedure codes: TK800, TK829, TK810,
 - ICD-10 code: Z49

PFIZER CONFIDENTIAL

- history of kidney transplant (any records until index)
 - procedure codes: KAS10, KAS20
 - ICD-10 code: Z94.0
- history of nephrectomy (any records until index)
 - procedure codes: KAC*, KAD*, KAS40, KAS41
 - ICD-10 code: Z90.5
- performance status at index
 - Karnofsky (converted from Zubrod/ECOG)
- time from initial diagnosis of RCC to initiation of treatment for metastatic RCC
- various laboratory measures (e.g. hemoglobin, serum calcium, neutrophiles, thrombocytes, creatinine, albumin, eGFR)
- smoking status (if available in structured format)
- histology (if available in structured format)
- BMI (if available in structured format)

For categorical variables, the number (N) and the proportion (%) of patients in each class will be reported. For continuous normally distributed variables, mean and standard deviation (SD) will be reported. For continuous, non-normally distributed variables, median, the 1st quartile and the 3rd quartile will be reported.

The difference between strata will be tested using chi-squared/Fisher's exact test (categorical variables), t-test (continuous normally distributed variables) and Kruskal-Wallis test (continuous non-normally distributed variables).

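### A C64 code alone defines RCC, so a patient whose recorded histology is not RCC stays in the local and untreated-mRCC columns of primary objective 1

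*Combined protocol and SAP*

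**What the plan says.** **Entry.** Section 7.1 identifies adults "with RCC diagnosis (C64*; '*' indicates any number) will be identified from the data lake of HDSF". Section 7.4 adds: "The patient population will be selected from the health records at the data lake of HDSF based on diagnosis data". Pathology data are then collected for the cohort already identified. Section 7.2.1 asks for "Diagnosis of renal cell carcinoma (ICD-10: C64) during 1.1.2010-31.12.2021", adult age and residence in the district. For patients without metastatic disease, 7.2 sets the index as follows: "For RCC patients, the date of the first record of RCC diagnosis (ICD-10: C64").

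**Exclusions.** For the characteristics cohort, 7.2.2 removes patients with metastatic RCC before 2010 and "Prevalent RCC patients (i.e. diagnosis of RCC before 1.1.2010) if there is no records of metastatic disease during 2010-2021". It says nothing about histology.

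**Histology.** Table 2 in 7.3 lists "PAD histology (if available in structured format") with the role PO1 only. Other variables in the same table, such as diagnoses, medications and staging, carry patient-inclusion roles. In 7.7.1, "histology (if available in structured format") is one of the characteristics to be summarised.

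**RCC and kidney cancer.** Section 5 describes RCC as "the most common type of kidney cancer occurring in Western communities", so the protocol recognises that other types exist.

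**The concern.** Primary objective 1 is to characterise patients with RCC. The plan defines RCC by a diagnosis code and also collects the variable that could contradict that code, but has no rule for when the two disagree. The histology row could then list non-RCC tumours inside a column headed RCC, and those patients would also count in every other row: age, sex, nephrectomy, laboratory values and performance status.

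The columns are not equally exposed. Local patients enter on the code alone. Untreated mRCC patients need one further marker, but an oncologist visit with the RCC code as main diagnosis is enough. Section 7.2.1 justifies that marker by a statement about RCC patients, which need not hold for a patient with another kidney tumour. Treated mRCC patients must also have received a drug from Table 3, which makes a non-RCC case much less likely.

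**Working it through.** **1. Follow one patient through the rules.** Take an adult resident with a C64 code in the study period and a structured histology entry showing a tumour other than RCC.

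- 7.2.1: code, age and residence are met, so the patient is included.
- 7.2.2: no diagnosis before 2010, so no exclusion applies.
- 7.2, placement: with no marker of metastasis, the patient is local RCC. With an oncologist visit under that code and no Table 3 drug, the patient is untreated mRCC. With a Table 3 drug, treated mRCC.
- Table 2 and 7.7.1: histology is reported as a characteristic. The patient counts in that row and in all the others.

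No step removes the patient. This holds whatever the number of such patients.

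**2. Reproduce the plan's size figures (7.5).** About 1,100 RCC patients, of whom 20-50% become metastatic:

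- 1,100 × 0.20 = 220 and 1,100 × 0.50 = 550, which matches the stated 220-550.
- The complement is 1,100 − 550 = 550 to 1,100 − 220 = 880 patients without metastatic disease.

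So on the plan's own figures, half or more of the characteristics cohort (550/1,100 = 50% to 880/1,100 = 80%) would enter on the code alone.

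**3. What contamination does to a reported figure.** Let *c* be the share of a column that is not RCC, and *d* the difference in a characteristic between those patients and true RCC patients. The reported proportion is (1 − c)·p + c·(p + d) = p + c·d, so the shift is c × d. The documents give neither *c* nor *d*. Under assumed values:

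| Assumed share *c* | *d* = 5 points | *d* = 10 points | *d* = 20 points |
|---|---|---|---|
| 5% | 0.25 | 0.5 | 1.0 |
| 10% | 0.5 | 1.0 | 2.0 |
| 15% | 0.75 | 1.5 | 3.0 |

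Shifts are in percentage points. Under these assumptions the distortion of a single row is modest. The histology row is the exception: there the non-RCC share appears directly as *c*, among patients with structured histology.

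**The case against.** **The documents label C64 as RCC throughout and never say that other tumours share the code.** This is correct. Section 5 shows only that RCC is one type of kidney cancer. That C64 is wider than RCC is a general assumption about the code. The point does not need a rate, however: it is that a recorded non-RCC histology has no consequence.

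**A reader might infer that a large part of the local column is not RCC.** If 3-15% of the 1,100 are assumed not to be RCC (33-165 patients) and all are local, they make up 33/880 = 3.8% to 165/550 = 30% of that column. The documents do not support this range:

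- The 3-15% has no source in them.
- The 1,100 comes from cancer-registry statistics. It is not a count of C64 codes in the data lake, so codes entered on suspicion and later ruled out need not be among them.
- The 30% combines the highest error rate, the highest metastatic share and all errors in one column.
- The oncologist-visit rule would move some of these patients to untreated mRCC.

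**A reader might also infer that many codes are unconfirmed single entries.** One record does suffice, but this follows from the index rule and the absence of any count, not from an explicit statement. Nothing in the documents says how often it happens.

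**The plan already has checks.** Section 7.8 provides for clinical review of data integrity and plausibility, 7.9 concedes that entries may be wrong, and the histology row would show the problem to readers. These stand as disclosure and checking. None of them says what happens to a patient with non-RCC histology, and the only misclassification that 7.9 names concerns treatment lines.

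**Histology may be too sparse to use.** It may be. But 7.2.1 uses AJCC stage for inclusion while noting that it may be missing for some patients, so incomplete structured data are already accepted for eligibility.

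**The effect on the study is limited.** This also stands: every other objective uses treated mRCC only.

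**Conclusion.** The point holds as a gap in the case definition. A C64 code makes a patient an RCC case, and the histology that the study collects cannot undo it. The local and untreated-mRCC columns of primary objective 1 are exposed; treated mRCC is largely protected. How many patients are affected is unknown, and no percentage should be quoted as a finding. The shifts worked out above rest on assumed shares and differences. The case for a change is that a primary objective is affected, the remedy uses data already requested, and the current plan neither resolves nor counts the conflict. It does not put the treatment-pattern or survival results in doubt.

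**What to change.** - **7.2.1:** keep C64 as the screening code.
- **7.2.2:** for both cohorts, exclude patients whose structured kidney-tumour histology shows a diagnosis other than RCC.
- **Table 2:** change the role of histology to patient inclusion/exclusion and PO1, and list before data release which entries count as RCC.
- **Main table:** keep patients without structured histology. This respects the rule in 7.7 that missing values do not exclude a record.
- **Reporting:** give histology coverage and the number excluded.
- **Sensitivity analysis:** repeat the primary objective 1 table in patients with histology-confirmed RCC and show it beside the main table.
- **7.9:** name RCC case misclassification as a limitation.

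A rule requiring a repeat C64 record is optional. It addresses unconfirmed codes only, because a patient with another kidney tumour could well have the code recorded repeatedly.

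**Cost.** Protocol wording and a few lines of code. The exclusion acts only where structured histology exists, so it may remove few patients. The confirmed subset may be smaller and selected, which is why it belongs in a sensitivity analysis and should not replace the main table.

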6. RESEARCH QUESTION AND OBJECTIVES

The objective of this study is to describe the characteristics and treatment outcomes of patients with advanced/metastatic RCC with medical records in the HDSF data lake. In the first primary objective, all RCC patients (with local or metastatic disease) are analyzed (treated and non-treated mRCC patients separately). In all other objectives, only treated mRCC patients will be analyzed. The objectives of the study are to:

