7.2. Setting

The target population of this study is adult patients with RCC and medical records available at HDSF data lake. Estimated number of patients in this study is 220-550. The inclusion criteria is a diagnosis of renal cell carcinoma (ICD-10: C64) between January 2010 and December 2021 (Figure 1). Advanced/metastatic disease stage (mRCC) will be assessed based on ICD-10 diagnosis code for metastasis (C77*-C79*), American Joint Committee on Cancer (AJCC) stage 4, visit to oncologist (specialty code 65), or initiation of treatment for mRCC.

[figure not shown]

Figure 1. Graphical illustration of study time windows and corresponding analyses.

The data collected has been generated as part of standard clinical care, treatment, and follow-up of patients with RCC. In accordance with the Finnish Act on Secondary Use of Health and Social Data 552/2019 (in Finnish: Laki sosiaali- ja terveystietojen toissijaisesta käytöstä), health registry data can be processed in scientific studies without patient consent. The purpose of this act is to establish conditions for the effective and secure processing of, and access to, personal health and social data for certain secondary purposes, such as research and statistics, innovation and development, knowledge management, teaching and authority planning. Thus, the Secondary Act creates a clear legal basis for the use of such registered data for research and innovation related to, for example, the health and well-being of citizens, the prevention of

disease and the development of new treatment methods. This relatively new legislation is also a welcome unification of the fragmented Finnish national rules regarding the use of healthcare and social welfare data. In addition, it takes into consideration current data protection requirements.

In the primary objective 1 (characteristics), all RCC patients will be analysed (local and metastatic diseases separately), while in the other objectives only treated mRCC patients will be analysed. Therefore, there are two cohorts to be analysed: 1) characteristics cohort (including all RCC patients), 2) mRCC cohort (including only treated mRCC patients).

Definitions for mRCC cohort

Index: Date of the first mRCC diagnosis; date of the metastatic disease identified as first of the following after the initial RCC diagnosis

- ICD-10 diagnosis code (C77*-C79*) for metastatic disease
- AJCC stage 4
- Visit to oncologist (specialty code 65) with RCC as main diagnosis

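### A C77-C79 code that need not relate to RCC can define metastatic RCC and set its index date, mainly affecting the non-treated mRCC group

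*Combined protocol and SAP*

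**What the plan says.** Section 7.2.1 defines metastatic RCC by any one of four records. The first is "ICD-10 diagnosis code for metastasis (C77*-C79*), or". The others are AJCC stage 4, "a visit to oncologist (specialty code 65) with RCC as main diagnosis, or", and initiation of treatment for mRCC.

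Section 7.2 uses the same list for the index date, taken as the "date of the metastatic disease identified as first of the following after the initial RCC diagnosis". The code entry there reads "ICD-10 diagnosis code (C77*-C79*) for metastatic disease" and the visit entry "Visit to oncologist (specialty code 65) with RCC as main diagnosis".

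Section 7.2.1 also remarks: "In Finland, the ICD-10 codes for metastatic disease are rarely used". It presents the oncologist visit as the proxy for that reason.

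Under section 6, in the first primary objective "all RCC patients (with local or metastatic disease) are analyzed (treated and non-treated mRCC patients separately". All other objectives use treated mRCC patients only, because section 7.2.2 removes from the mRCC cohort "Patients without treatment for mRCC (see Table 3 for details".

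**The concern.** Codes C77-C79 record a secondary tumour without naming the primary. The plan ties the oncologist visit to RCC but gives the code no such tie beyond time order. Section 7.2.2 has no rule for a second primary cancer, and the limitations in section 7.9 do not mention metastases from another cancer.

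Three results could be affected:

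- **Non-treated mRCC group (primary objective 1).** A local-RCC patient with another cancer's metastases joins this group, leaves the local group, and has age, laboratory values and history summarised at a false metastasis date.
- **Cohort entry.** Section 7.2.2 drops patients diagnosed before 2010 unless metastatic disease is recorded in 2010-2021. An unrelated code could keep in a pre-2010 local-RCC patient who should be excluded.
- **Index date in true mRCC.** An unrelated code that precedes the real metastasis moves the index earlier. This affects overall survival where it is counted from mRCC diagnosis (section 6.1, objective 3) and yearly costs from index (section 7.7.5).

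**Working it through.** **Following the rule.** Take a patient with local RCC diagnosed in 2013 and another cancer that metastasises in 2017, coded C78.

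1. The code follows the RCC diagnosis and lies within 2010-2021, so section 7.2.1 makes the patient mRCC.
2. Section 7.2 sets the index in 2017, since the code is the first qualifying record.
3. No exclusion in section 7.2.2 applies to the characteristics cohort.
4. With no Table 3 drug, the patient is not in the mRCC cohort and appears only as non-treated mRCC in primary objective 1.

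The phrase metastatic RCC at the head of the list does not prevent this, because the code is itself the operational definition.

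**The plan's own figure (section 7.5).** 1,100 × 0.20 = 220 and 1,100 × 0.50 = 550, which reproduces the stated 220-550. The complement is 880 to 550 non-metastatic patients.

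**A second base (section 5).** There, 20-30% are metastatic at diagnosis and a further 20% of localised cases relapse.

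- Non-metastatic: 1,100 × 0.80 × 0.80 = 704; 1,100 × 0.70 × 0.80 = 616.
- mRCC: 1,100 − 704 = 396; 1,100 − 616 = 484.

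**Illustration.** The documents give neither of the two rates needed, so both are assumptions: a share q = 1-5% of non-metastatic patients carrying an unrelated C77-C79 code, and a share u = 30-50% of true mRCC patients untreated. All false cases are taken to be untreated. With M true mRCC patients and L non-metastatic patients:

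false share of the non-treated group = qL / (uM + qL)

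| Base | M | L | q | u | Calculation | Share |
|---|---|---|---|---|---|---|
| Section 5, low | 484 | 616 | 1% | 50% | 6.16 / (242 + 6.16) | 2% |
| Section 5, high | 396 | 704 | 5% | 30% | 35.2 / (118.8 + 35.2) | 23% |
| Section 7.5, low | 550 | 550 | 1% | 50% | 5.5 / (275 + 5.5) | 2% |
| Section 7.5, high | 220 | 880 | 5% | 30% | 44 / (66 + 44) | 40% |

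The pre-2010 patients may lie outside the 1,100 and are not counted here.

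**The case against.** **The codes are rare.** The remark that they are seldom used in Finland is not limited to RCC, so it may hold down false codes as well as true ones. A false case needs a second primary, metastasis after the RCC diagnosis and within the study window, and a seldom-used code. This stands, and it makes the 5% end doubtful. A reader might infer the reverse, that rarity gives false codes more weight. That can hold at most among patients who enter by code alone. Those who enter by an RCC oncologist visit dilute the error.

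**Existing review covers it.** Section 7.8 provides for plausibility checks with a clinical expert, and section 7.9 for a clinician's advice on treatment lines. Neither is directed at metastases from another primary.

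**Requiring a link could lose true cases.** It could, but by the protocol's own premise few. Section 7.2.1 holds that RCC patients see an oncologist if, and only if, the disease has spread. A true mRCC patient should then usually qualify by that route too.

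**The treated cohort.** A reader might infer that other cancers' deaths, lines and costs enter primary objectives 2-3 and secondary objective 2, because Table 3 identifies drugs by ATC code. The documents do not support that as a consequence of this rule. A patient given a Table 3 drug for another cancer could enter by the treatment criterion with no C77-C79 code at all, which is a separate question of drug indication. The criterion is also worded as treatment for mRCC. For outcomes by line, time starts at treatment initiation, so they are largely protected.

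**Conclusion.** The rule as written is flawed. A C77-C79 code alone, linked to RCC only by coming later, defines mRCC and can set its index date. The main effect is on the non-treated mRCC group of primary objective 1. A lesser effect is too early an index in some truly metastatic treated patients, for results counted from mRCC diagnosis. Section 7.2 also says that the index for treatment outcomes is treatment initiation, so survival is exposed only where it is counted from mRCC diagnosis.

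The size is not established. The ranges of about 2-23% and 2-40% rest wholly on the assumed 1-5% and 30-50%, and on all false cases being untreated. A reader might combine the 704 non-metastatic patients from section 5 with the 220 mRCC patients from section 7.5 and arrive at about a third. Those figures do not belong together: they sum to 924, not 1,100. The case for a change is that the rule misclassifies by construction and the remedy is cheap, not that a large bias has been shown.

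**What to change.** In sections 7.2 and 7.2.1, let a C77*-C79* code qualify, and set the index, only if one of these holds:

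- C64 is recorded on the same contact; or
- the patient has no other primary malignancy code (C00-C76 or C81-C97, other than C64 and C44) before it or within 90 days after it. C80 is left out because a malignancy of unspecified site does not establish another primary.

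A patient whose code fails is classified and indexed by the remaining criteria: AJCC stage 4, RCC oncologist visit, or treatment initiation. If none is met, the patient is treated as not having mRCC.

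Report the number failing. Repeat primary objective 1 (local, treated and non-treated groups) and the analyses counted from the mRCC index under the rule as now written.

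**Cost.** This is a code-list rule on data already planned: section 7.2 uses the main diagnosis of a visit, and Table 2 lists ICD-10 co-diagnoses before and after index. A few true mRCC patients with a second primary, possibly a distant one, and no C64-linked contact will move out of the main analysis. The repeat makes that visible. If the number failing is near zero, reporting it settles the question.
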